a participant completes all study activities, this equipment will be collected at the final home visit (H2) or once the self-management visits are completed coordinators will schedule to come pick up the equipment from the family's home. If a participant is discontinued from the study early due to lost to follow-up, study staff will follow the *Study Discontinuation MOP* in order to collect the loaned iPad and Cradlepoint. The actions taken will include: phone calls, text messages, emails, letters mailed to the home, and home visits. If the equipment is not recovered, a certified letter will be sent to the home with instructions to return the iPad and Cradlepoint with a copy of the *Telehealth Agreement Form* that was signed at the first Home Visit (H1). Per the signed *Telehealth Agreement Form*, families are responsible for notifying CCHMC if the iPad is lost or stolen. "iPads that are lost or stolen will be reported to the CCHMC Protective Services Department and to the appropriate Police Department". If the equipment is not returned after all steps in the *Study Discontinuation MOP* have been followed, the Telehealth department at CCHMC will be notified that the equipment was not recovered.

9. DATA ANALYSIS/METHODS:

Study Outcomes:

The adolescent's asthma outcomes and adherence will be measured at baseline and during the clinical visits or study telephone calls once a month for a total of 12 months. Outcomes will be measured during the monthly medical visits using a computerized TreatSmart program based on the NAEPP asthma guidelines which was adapted by the CCHMC Asthma Center database team from the Inner City Asthma Coalition (Appendix C), ACT scores, and Propeller Health web-based inhaler cap monitoring sensor and mobile software management platform (Appendix B).

Primary Outcome:

Composite asthma severity index (CASI) score collected monthly during phone calls, home visits, and clinic visits over 1 year. The CASI is a severity score of symptom burden, exacerbations, healthcare utilization, lung function and dose of inhaled corticosteroids. This score will be collected and captured by the TreatSmart program.

Secondary Outcomes:

We will analyze the following outcomes: ACT score over past 4 weeks; rescue medication use, oral-steroid requiring exacerbations; healthcare utilization, lung function, dose of inhaled corticosteroids, and adherence of controller medication.

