These asthma related outcomes are commonly reported in both the adult and pediatric asthma literature and are endorsed by national asthma guidelines and the National Institutes of Health (NIH) asthma-outcome conference.

Data Analysis

We will use descriptive statistics to characterize the sample demographics. A descriptive analysis with calculation of means, medians, and standard deviations will be performed for each continuous measure; categorical measures will be examined with percentages. If necessary, we will log-transform non-normal data; however if a normal distribution cannot be attained we will use nonparametric statistics. We will use paired t-tests to evaluate the null hypothesis that there was no change in the primary outcome (CASI score) while participants are blinded to data collected by the Propeller medication sensor in the first month of participation. Nonparametric methods will be used if the assumptions for paired t-tests are violated. The primary analyses will test whether this interventional program improves CASI scores (from completion of the first month to study exit). Linear mixed effects models with a random effect for subject assessed changes in primary asthma endpoints each month across the 1 year study or upon exit. Participants with one or more observations will be included in the analysis. All statistical analyses will be implemented in SAS 9.3 (SAS Institute, Cary, NC) and use a significance level of 0.05. Potential confounders identified from the literature, such as age, gender, season of enrollment, severity of asthma at baseline, smoke exposure, environmental exposures and atopic status will be adjusted in the analyses. The REML model used for these analyses requires that any missing data are “missing at random” (MAR) to yield valid estimates. To account for the presence of possible non-ignorable missing data, pattern- mixture modeling will be applied for these analyses.

The secondary analyses will look at the ACT score, rescue medication use, oral-steroid requiring exacerbations, healthcare utilization, lung function, dose of inhaled corticosteroids, and adherence of controller medication. Linear mixed-effect models will be used to compare the continuous outcomes such as exacerbations. Generalized linear mixed effect models will be used to compare the discrete outcomes such as health system utilization, both accounting for repeated measurement over time while adjusting for confounders.

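### The log-then-nonparametric rule does not suit zero-prone outcomes such as exacerbations, and the plan does not say that it leaves the mixed models alone

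*Combined protocol and SAP*

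**What the plan says.** All the relevant text is in Section 9 (Data Analysis/Methods).

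- After the sentences on descriptive statistics comes the general rule: "If necessary, we will log-transform non-normal data; however if a normal distribution cannot be attained we will use nonparametric statistics". It names no normality test, no scale for the check (raw, per visit or residual), no constant for zeros and no nonparametric method.
- The first-month paired t-test on CASI has a fallback of its own: "Nonparametric methods will be used if the assumptions for paired t-tests are violated".
- The primary analysis is a linear mixed model with a random subject effect on monthly data, adjusted for a list of confounders. Its analysis set is stated: "Participants with one or more observations will be included in the analysis". Its missing-data basis is stated too: "The REML model used for these analyses requires that any missing data are" missing at random, with pattern-mixture modelling added.
- The primary outcome is "Composite asthma severity index (CASI) score collected monthly during phone calls, home visits, and clinic visits over 1 year". The section gives no range, SD or share of zeros for it.
- The secondary outcomes include "rescue medication use, oral-steroid requiring exacerbations; healthcare utilization". Exacerbations are given as the example of a continuous outcome for linear mixed models. Health system utilization is given as the example of a discrete outcome for generalized linear mixed models. Rescue use is assigned to neither class.

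**The concern.** A linear mixed model needs roughly normal residuals and random effects. It does not need normal raw data, so a rule driven by the shape of the data can alter an analysis that was sound.

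For a count that is mostly zero, each step of the rule goes wrong. The log of zero is undefined, and without a stated offset those records become missing. They are the best outcomes. With an offset, the zeros remain a single spike, so the rule moves on to nonparametric statistics. The ordinary versions of those tests do not handle monthly repeated measures, adjust for confounders or use incomplete follow-up. Section 9 promises all three.

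At stake are the size of the effect reported for exacerbations and rescue use and, if the rule were carried over to CASI, which children the primary test includes. Because the rule names no test, scale or method, those choices would be made after the data are seen.

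**Working it through.** The documents give no power, normality or event-rate figure, so there is nothing to reproduce. From the documents come 30 children (Section 8; Section 6 gives 30-50), monthly measurement over 12 months, and the model assignments above. The rates, dispersions and missing-pair shares below are assumptions, shown as ranges.

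**1. How often a monthly exacerbation count is zero.** For an annual rate r:

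- Poisson: P(0 in a month) = exp(-r/12). For r = 0.5, exp(-0.0417) = 0.959. For r = 4, exp(-0.333) = 0.717.
- Negative binomial with k = 1: P(0) = 1/(1 + r/12). For r = 0.5, 0.960. For r = 4, 0.750.

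So 72-96% of child-months are zero. Over a full year, the number of 30 children with no event is:

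- Poisson, 30 x exp(-r): 18.2 at r = 0.5 and 0.5 at r = 4.
- Negative binomial, 30/(1 + r): 20 at r = 0.5 and 6 at r = 4.

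A plain log removes every one of these zero records.

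**2. Whether an offset rescues the log.** log(x + c) sends all zeros to the single value log(c). The transformed data therefore still have 72-96% of their values at one point. No choice of c makes that normal, and the argument does not depend on pooling visits. As a check, Shapiro-Wilk on log(x + 1) for 30 children x 12 months rejected normality in 100% of simulated data sets at every rate from 0.5 to 4. Under the stated rule, the next step is nonparametric statistics.

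**3. Rescue use, if it were logged.** Assume a negative binomial count with the mean falling from 4 to 2, a true ratio of 0.50. P(0) = (k/(k + m))^k, where m is the mean and a smaller k means more spread. The geometric mean is taken over positive values only.

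| k | Share zero, m = 4 | Share zero, m = 2 | Geometric-mean ratio, positives | Fall shown |
|---|---|---|---|---|
| 0.5 | 0.33 | 0.45 | 0.68 | 32% |
| 1 | 0.20 | 0.33 | 0.65 | 35% |
| 2 | 0.11 | 0.25 | 0.63 | 37% |

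The true fall is 50%. Part of the improvement is the move to zero, and the log of positive values cannot see it.

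**4. CASI, only if a paired nonparametric test replaced the mixed model.** Children lost = 30 x share without a month-1/exit pair: 30 x 0.05 = 1.5, and 30 x 0.30 = 9. With 50 children the range is 2.5-15. The mixed model under the one-or-more-observations rule would keep those who have any score.

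**5. Whether CASI needs to leave the mixed model.** In simulations of skewed whole-number scores (13 visits, within-child correlation 0.3-0.7, 4,000 runs per setting), the random-intercept slope test at 0.05 had a type I error of 4.5-5.5%. Non-normality of that size gives no reason to abandon the model.

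**The case against.** The strongest defence concerns scope. The sentence sits between the descriptive statistics and the paired t-test. The mixed model comes later with no normality condition attached, and nothing says that nonparametric statistics replace it. Read in that order, the section does not contradict itself. This stands, and it limits what can be claimed about CASI. It does not settle the matter, because means and medians need no normality rule and the paired t-test already has its own. The mixed models are the natural remaining target, and they are not excluded.

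A reader might infer four stronger things, none of which the documents support:

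- *The rule deletes zeros.* That follows from a plain log, but the text neither says it nor rules out an offset. For CASI, the documents do not show that zeros occur at all.
- *The rule would almost always displace the CASI mixed model.* Pooled whole-number scores do fail Shapiro-Wilk in about 99% of simulated data sets, but that is a reaction to rounding. Rounded scores with no child effect fail about as often, while continuous scores that follow the model exactly (SD 3.5, correlation 0.5) fail in about 17%. The plan specifies neither pooling nor a formal test.
- *The rule contradicts the inclusion rule.* It does so only if a paired fallback replaces the mixed model.
- *Healthcare utilization is lost as well.* It is already assigned to a generalized model.

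It is also fair to say that the event rates and dispersions are assumed. They set the size of the effect. The direction does not depend on them when zeros become more common.

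**Conclusion.** The point holds in a limited form. It is firmest for exacerbations, which the plan expressly assigns to a linear model: with 72-96% of child-months at zero (assumed 0.5-4 events per child-year), neither step of the rule gives a usable version of the promised analysis. For rescue use the risk is the same but depends on a classification the plan does not make; if logged, a 50% fall would be reported as 32-37% under the assumed distributions. For CASI the plan's model is sound as written, and the loss of 1.5-9 of 30 children arises only on one reading of the rule and an assumed 5-30% without a pair. This should be corrected before analysis, but it does not invalidate the primary analysis.

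**What to change.** In Section 9 (Data Analysis):

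1. State that the log/nonparametric rule does not replace the mixed models.
2. Judge model assumptions on residuals of the fitted model.
3. Keep CASI in the linear mixed model on its original scale. Label any robust, bootstrap (resampling children) or nonparametric analysis as sensitivity.
4. Analyse exacerbations and rescue use with a generalized linear mixed model with a log link (Poisson or negative binomial). This keeps the zeros and does not log the data. Move exacerbations out of the continuous class and assign rescue use explicitly.
5. Keep the signed-rank test only for the first-month paired comparison.

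The cost is SAP wording and a little programming, with no extra data. The count model does not cure sparse data: the assumed rates give 30 x 0.5 = 15 to 30 x 4 = 120 exacerbations over the year if all 30 children are followed, so the SAP should also say which confounders that model will carry.

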4. STUDY DESIGN

We will conduct study visits in the Schubert clinic to determine and quantify known molecular, genetic, genomic, epigenetics, immunologic, and exposure biomarkers that will help elucidate molecular disease endotype within the DTT phenotype (Figure 1). This information will be used along with clinical, psychosocial, and adherence data to develop

a personalized treatment plan. We will track disease outcome metrics including exacerbations, symptom-free days, and a validated asthma composite control score to determine the effectiveness of this personalized approach (summarized in Figure 1).

A number of interventions will be incorporated based on information collected on questionnaires on personal and family medical history, history of environmental exposures, previous and current residential and school addresses, depression, anxiety, dietary intake, adherence, medical literacy, and perceived quality of life, medical visits, use of a commercially available inhaler cap monitoring sensor, a mobile software management platform that tracks adherence of asthma medications, mobile based telehealth adherence problem-solving interventions, biomarker assays and home trigger assessment and remediation.

This proposal is funded through a CCHMC ARC award.

5. DURATION:

Duration for the participants will be 12 months. We will continue to follow asthma outcomes via the patient's medical record for an additional 12 months. Participants will be enrolled in the study during the 24 months of the project. If additional funds are awarded, the enrollment period may be extended to a third funding year. Data analysis will be performed 6 months after the last participant completes the project.

6. SELECTION & RECRUITMENT OF PARTICIPANTS:

A. Number of participants

Patient Population: 30-50 6-17 year old children with uncontrolled moderate-severe persistent asthma without significant chronic disease other than allergic disorders.

B. Inclusion/Exclusion criteria

Inclusion

- age 6-17 years; history of provider-diagnosed asthma;
- Meets one of the following definition for NAEPP guidelines uncontrolled moderate persistent asthma or severe persistent asthma in the past 12 months:
 - NAEPP step 3-4 with one of the following criteria in the past 12 months:
 - two ACT scores <20
 - ≥ 1 UC/ED visit or hospitalization for asthma
 - ≥ 2 prednisone bursts
 - NAEPP step 5-6

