If a consent/assent form is updated and requires a new signature, coordinators will go over the changes via either a scheduled monthly phone call or scheduled study visit (depending on which visit occurs first) and participants and guardians may be re-consented by either eConsent (as stated in the section above) or by signing a copy of the consent/assent either in person or sent through the mail. Participant's and guardians will be given ample time to read through the new consent/assent and will be able to call and ask questions etc. once they have been able to read through the consent/assent.

For participants under age 18, age of assent will be determined by the IRB and those assenting will sign after all questions are answered.

For non-English speaking participants

Because this is a small pilot and heavily dependent on English fluency for teleconference interviews and questionnaires, only participants who are fluent in English will be enrolled. If a parent is non-English speaking, the PI will determine if the subject can be enrolled based on subject's fluency. If a non-English speaking parent will be giving Parental Permission, the research team will use a short form consent process as per CCHMC SOP 41-1.8. The approved long consent form will serve as the summary of the research.

8. STUDY PROCEDURES:

See Appendix A.

The study length is 12-15 months. 30 participants will be enrolled over a 9 month period. Propeller and TreatSmart program screenshots are located in Appendix B and C.

CCHMC Visit 1 (V1)- Baseline Medical Visit: This visit will be conducted at CCHMC.

The coordinator will consent the parent/legalguardian(s) and (if applicable) obtain assent from the child/adolescent. Baseline questionnaires will be completed by a parent/guardian and the participant, and the study visit procedures will be explained by the study coordinator.

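### The plan does not say which CASI contrast decides the primary analysis, or what study exit means for a child who leaves early

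*Combined protocol and SAP*

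**What the plan says.** All of this is in the combined protocol and SAP.

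- **Primary outcome (section 9, Primary Outcome).** CASI is a "score collected monthly during phone calls, home visits, and clinic visits over 1 year". Its components include exacerbations and healthcare utilisation.
- **Primary test (section 9, Data Analysis).** The question is whether the programme improves CASI "from completion of the first month to study exit". That names one comparison.
- **Model (next sentence).** Linear mixed models with a random effect for subject "assessed changes in primary asthma endpoints each month across the 1 year study or upon exit".
- **Level.** All analyses "use a significance level of 0.05". Sidedness and multiplicity control are not mentioned.
- **Missing data.** Anyone with at least one observation is included. The model is fitted by REML assuming missing at random, and pattern-mixture models are added for non-ignorable missingness.
- **Leaving the study (section 8, Study Termination).** Participation ends after four or more severe exacerbations, or more than two asthma hospitalisations. It also ends when a family cannot be reached.
- **End of study for completers (section 8 and Appendix A).** The final visit may be H2 or the optional V3. Both are placed at month 12, with windows of ±4 and ±16 weeks.

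**The concern.** Two things needed to define the primary result are missing.

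**The decisive contrast.** One sentence gives a single comparison. The next gives change at every month or at exit. Time could enter the model as a slope, as a categorical month with one chosen contrast, or as a set of monthly contrasts. These answer different questions. In an uncontrolled pilot of about 30 children, leaving the choice open means the primary claim can be selected after the data are seen.

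**The meaning of exit.** For a child who stays, exit is roughly month 12. For a child who leaves at month 4, it could mean the last observed score, or only that observation stops there. On the first meaning, the endpoint mixes short and long follow-up. It also depends on outcome, because the termination rule acts on events that CASI itself counts.

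**Working it through.** The documents give no power, effect-size or familywise-error figure, so there is none to reproduce. The check asks what follows if the open choice is used.

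**Inputs from the documents**
- Level 0.05 (section 9).
- Sample size: "30 participants will be enrolled over a 9 month period" (section 8), or "30-50 6-17 year old children with uncontrolled moderate-severe persistent asthma" (section 6). I used N = 30 and N = 50.
- Monthly CASI gives 11 contrasts (months 2-12 against month 1), or 12 (months 1-12 against day 1). The number of tests is inferred from the schedule and is not stated.

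**Assumptions (not in the documents)**
- No true change, complete data, two-sided tests.
- Correlation between visits j and k is c + (1 − c)ρ^|j−k|, with (c, ρ) = (0.5, 0), (0.3, 0.5), (0.3, 0.7) and (0, 0.9).

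**Step 1: independence, as a ceiling.** 1 − 0.95^11 = 43.1%; 1 − 0.95^12 = 46.0%. This is too high, because the contrasts share a reference visit.

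**Step 2: shared reference under a random intercept.** With residual variance σ², each contrast has variance 2σ² and any two have covariance σ², so their correlation is 0.5. With 1,000,000 draws, the chance of at least one |z| > 1.96 is 30.3% for 11 contrasts and 31.9% for 12. Counting only false improvement, it is 15.2% and 16.0%.

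**Step 3: simulated null trials** (6,000 per setting; ranges cover N = 30 and 50, and 11 and 12 contrasts).

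| c, ρ | Any month, random-intercept model | Any month, paired contrasts | Last month only, random-intercept model | Last month only, paired contrast |
|---|---|---|---|---|
| 0.5, 0 | 29.4-31.7% | 30.9-32.2% | 4.6-5.1% | 4.5-5.3% |
| 0.3, 0.5 | 31.1-32.1% | 27.4-30.1% | 6.9-7.1% | 4.4-5.3% |
| 0.3, 0.7 | 30.5-33.8% | 26.2-27.6% | 9.3-10.8% | 4.6-5.0% |
| 0, 0.9 | 31.6-32.6% | 22.2-23.8% | 16.1-16.8% | 4.8-5.3% |

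The any-month rate runs from about 22% to 34%. In a repeat run with 8,000 trials per setting, false improvement alone was 11-17%, about half the two-sided rate.

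**Step 4: one contrast.** With the variance estimated correctly (paired contrast), the error is 4.4-5.3%. With only a random intercept it rises to about 7-17% when scores are serially correlated. That model gives every pair of visits the same difference variance, whereas month 12 and month 1 are the least correlated pair, so the standard error is too small.

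**Step 5: keeping all months as primary claims.** Bonferroni over 11 contrasts would need 0.05/11 = 0.0045 each.

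**Step 6: exit as last score.** The bias depends on the dropout rate, the CASI standard deviation and how strongly leaving follows the score. None is given, so I put no number on it. Its sign is also open: leaving after bad scores pushes the change towards worsening, and leaving when well pushes it towards improvement.

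**The case against.** The plan does name one comparison, month 1 to exit, and a mixed model on monthly data can deliver one test. The 0.05 level is a general statement, and no sentence says that any single month counts as success. If only the named contrast decides, and its covariance is right, the error is 5%. A reader might infer that each month is a separate primary test at 0.05. The text does not say so, and the 22-34% is conditional on that use.

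A reader might also infer that an early leaver's last score is carried to month 12. No such rule is written. REML under missing at random uses the observed months and needs no substituted value. Pattern-mixture modelling is the plan's own provision for leaving that depends on outcome. The plan therefore does not contradict itself here; a conflict arises only if exit is read as a last-score endpoint.

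It is also fair that a small pilot needs less strict multiplicity control than a confirmatory trial.

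These points limit the claim but do not answer it. Missing-data methods do not say whether the target is month 12 or each child's last score, and nothing in section 9 says which of the available results decides.

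**Conclusion.** The concern holds as an unresolved ambiguity. Section 9 leaves open the decisive contrast, the form of time in the model and the meaning of exit, and it has no multiplicity rule.

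- **Size, if any month may be claimed:** about 22-34% chance of at least one false-positive month, and about 30-32% in the large-sample calculation under a random intercept. This rests on 11-12 two-sided contrasts, N = 30-50, complete data and assumed correlations.
- **Size, if one contrast is fixed:** 5% with a correct covariance, but about 7-17% with a random intercept alone under the assumed serial correlation of 0.5-0.9.
- **Exit as last score:** the endpoint would be outcome-dependent and of mixed duration, with a bias of unknown size and sign.

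The documents do not support saying that the plan tests each month at 0.05 as a primary claim, or that it carries last values forward.

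**What to change.** In section 9, Data Analysis:

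1. Name one primary contrast: the model-estimated month 12 minus month 1 mean CASI, from the REML mixed model using all scheduled scores with month as a categorical term, tested once at two-sided 0.05.
2. Replace the exit wording. Early leavers contribute their observed months only, and no exit score is moved to month 12. Say which visit supplies the month-12 score when both H2 and V3 take place.
3. Report the other months as estimates with confidence intervals, without significance claims.
4. Keep the pattern-mixture analysis as a sensitivity analysis of that same contrast.
5. State a covariance structure that allows serial correlation in place of a random intercept alone.

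The cost is SAP wording only, with no new data or visits. The downside is that a single favourable month can no longer be claimed as the primary result.

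### Season is named as a confounder only as season of enrollment, which cannot remove seasonal change from within-child CASI contrasts; the effect is small for on-time month-12 completers and larger mid-year and for early or off-schedule exits

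*Combined protocol and SAP*

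**What the plan says.** Section 9 (Primary Outcome) describes a "Composite asthma severity index (CASI) score collected monthly during phone calls, home visits, and clinic visits over 1 year". The Data Analysis text then states: "The primary analyses will test whether this interventional program improves CASI scores (from completion of the first month to study exit". The model is a linear mixed model with a random subject effect that "assessed changes in primary asthma endpoints each month across the 1 year study or upon exit". Tests "use a significance level of 0.05".

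The confounder list is open-ended: "such as age, gender, season of enrollment, severity of asthma at baseline, smoke exposure", and it ends with "environmental exposures and atopic status will be adjusted in the analyses". Neither the calendar season of each contact nor an interaction of enrollment season with study month is named in Section 9 or elsewhere. No control group or randomisation is described.

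On accrual, Section 8 says "30 participants will be enrolled over a 9 month period". Section 5 instead spreads enrollment over a 24-month project, with a possible extension into a third funding year.

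**The concern.** In a before-after study, anything that changes with calendar time can pass for a programme effect or hide one. The plan accepts that season matters by listing it, but the form it names is a between-child constant. The season that can bias a within-child change is the season at each contact, which differs between month 1 and most later months.

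If the covariate is used as written, a reader could take season as dealt with when the tested contrast has not moved. The same reasoning applies to the secondary outcomes analysed with mixed models (ACT, rescue use, exacerbations, utilization), although no size was worked out for them.

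**Working it through.** The plan states no effect size, SD or seasonal amplitude, so there is no figure of its own to reproduce.

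**Step 1: why the term drops out.** Write the model as y(i,t) = μ + τ(t) + γx(i) + u(i) + ε(i,t), where x(i) is season of enrollment. Then y(i,12) − y(i,1) = τ(12) − τ(1) + ε(i,12) − ε(i,1). Both γx(i) and u(i) cancel. With complete data the month contrasts are the same whatever γ is. With missing months a little between-child information enters, so small shifts are possible.

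**Step 2: what seasonal change remains.** Inputs from the documents: month 1 as the starting point, month 12 as planned exit, and accrual of 9 months (Section 8) or 24 months (Section 5). Assumed: an annual cosine of half-swing A CASI points, with enrollment spread evenly over a months. For two contacts g months apart, the largest mean seasonal difference over all positions of the seasonal peak is

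bias = A × 2 sin(πg/12) × F, with F = |sin(πa/12)| / (πa/12).

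Month 1 to 7: g = 6, 2 sin(π/2) = 2. Month 1 to 12: g = 11, 2 sin(11π/12) = 0.518. For a = 9: F = 0.707/2.356 = 0.300.

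| Even accrual over | F | Month 1 to 7 | Month 1 to 12 |
|---|---|---|---|
| 3 months (hypothetical bunching) | 0.900 | 1.80A | 0.47A |
| 9 months (Section 8) | 0.300 | 0.60A | 0.16A |
| 12 months (hypothetical) | 0 | 0 | 0 |
| 18 months (hypothetical) | 0.212 | 0.42A | 0.11A |
| 24 months (Section 5) | 0 | 0 | 0 |

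On a whole-month grid the 9-month row becomes 0.61A and 0.16A. A straight-line trend over the 11 months would carry 0.54A.

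**Step 3: off-schedule and early final contacts.** Appendix A gives the optional V3, which also collects CASI, a window of ±16 weeks. If every V3 fell 16 weeks early, the gap would shorten by 16 × 12/52 = 3.69 months to g = 7.31. With 9-month accrual that gives 1.88 × 0.300 = 0.56A. H2 has a window of ±4 weeks. Four weeks early is 0.92 months, so g = 10.08 and the bias is 0.964 × 0.300 = 0.29A. These are upper ends, since not every visit will be early. Children who leave earlier, through the exacerbation and hospitalization rule or loss to follow-up (Section 8, Study Termination), have still shorter gaps; the largest effect is at g = 6.

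**Step 4: simulation check.** REML mixed models with a random subject intercept, 30 children, 12 monthly scores, 9-month accrual and no true effect. Assumed: A = 1 point, between- and within-child SD 1.5 each. There were 150 runs for each of four seasonal peaks, with 0% and with 20% dropout.

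- Complete data: adding season of enrollment changed the month-7 contrast and the slope by less than 1e-13. With 20% dropout the largest change in any run was 0.04 points.
- Without a contact-season term, the mean spurious month-7 change reached 0.62 points with 31% false positives. The spurious 11-month linear change reached 0.58 points with 51% false positives. Both were the same, or nearly so, with season of enrollment in the model.
- With sine and cosine of the calendar month of each visit, the mean spurious changes fell to 0.09 or less (month 7) and 0.06 or less (linear). False positives for the linear change fell to 0.03–0.08.

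The simulated season has the same shape as the fitted terms, so this recovery is a best case.

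**The case against.** The strongest reply is that the headline result is hardly touched. An on-time completer's endpoints are 11 months apart, close to a full cycle. At the assumed 1-point half-swing, the 9-month bias is about 0.16 points. The standard error of the month-12 contrast under the assumed SDs is √(2 × 1.5²/30) = 0.39, so the bias is about 0.4 of a standard error. Month 7 is not a named endpoint, and no linear trend is specified. This stands, and it limits the point mainly to the monthly profile, early exits and off-schedule final visits.

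Second, 9-month accrual is not settled. Under the 24-month statement in Section 5, even intake makes the average bias about zero. This also stands, with the caveat that neither section promises even intake. Section 6.C expects about 70% of children to be identified at hospitalizations, the ED or specialty clinics, and others through school screening.

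Third, the confounder list is introduced by *such as*, so contact season or an interaction is not excluded. True, but neither is named. Environmental exposures do not fill the gap, because Appendix A schedules home samples only at H1 and H2.

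Fourth, season of enrollment may still explain differences in level between children. It need not be removed.

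**Conclusion.** The covariate as named does not do the job: as a main effect it cannot remove seasonal change from the within-child CASI contrasts. That part is algebra and does not depend on the assumptions.

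The size does. With even 9-month accrual the worst case is about 0.16A for month 1 to 12 in on-time completers and about 0.6A for month 1 to 7. It is larger than 0.16A for early exits and early final visits, and near zero for even 12- or 24-month accrual. All of this assumes a single annual cycle. A is not in the documents, and how seasonal a composite that includes lung function and inhaled-steroid dose would be cannot be judged from them.

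A reader might infer that the primary month-1-to-exit result is seriously biased, or that the false-positive rate is 31% or 51%. The documents do not support that. Those rates need a 1-point half-swing, 9-month intake, an unfavourable peak, and a mid-year contrast or straight-line trend. The 1.8A figure needs 3-month bunching, which no section describes. This is a worthwhile correction to the analysis wording, not a threat to the study's main result.

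**What to change.** In Section 9, for the primary and secondary mixed models, add the calendar season of each contact as a time-varying covariate, for example sine and cosine of contact date. Season of enrollment may be kept as a between-child term. Report the month-1-to-exit and monthly changes with and without the contact-season term. State whether study month is categorical or linear. Reconcile the 9-month accrual in Section 8 with the 24 months in Section 5.

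The cost is a sentence or two of wording and two model parameters. No new procedure is needed: the visit windows in Appendix A imply that contact dates are recorded, although the documents do not say so outright. If accrual is short, calendar time and study month are partly collinear. The standard errors will then widen, and the report should say so.
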